# 4.3 SECONDARY ENDPOINTS - EFFECTIVENESS

The study's secondary effectiveness endpoints are:

- The change in systolic pulmonary arterial pressure from baseline pre-procedure to post-procedure
- Incidence of adjunctive thrombolytic use

# 4.4 SECONDARY ENDPOINTS - SAFETY

The study's secondary safety endpoints will include incidence of adjudicated Adverse events, including:

- All-cause mortality through the 30-day visit (visit window = 30 days from procedure -5 / +15 days)
- Device-related SAE through the 30-day visit (visit window = 30 days from procedure -5 / +15 days)
- Symptomatic recurrence of pulmonary embolism through the 30-day visit (visit window = 30 days from procedure
   -5 / +15 days)

# 5 STUDY DESIGN

The study is a prospective, single-arm, multicenter study to evaluate the safety and effectiveness of the FlowTriever2 Catheter in patients eligible for endovascular treatment of acute PE.

### 5.1 NUMBER OF SITES AND SUBJECTS

Five to twelve (5-12) sites will participate in the Study. The total population for the Study is 50 subjects with no more than 20% enrollment at any one site. Sites are selected based on a variety of factors including, but not limited to, experience with endovascular techniques, access to required facilities and equipment, sufficiency and adequately trained personnel, and availability of potential subjects. The criteria used for determination will be documented.

### 5.2 STUDY DURATION

The subjects who meet the inclusion/exclusion criteria will be enrolled in the study. The enrollment period is expected to last over a period of approximately 12 months. Each study subject will actively participate for up to 30 days (-5 / +15 days) following treatment. Study participation includes screening, baseline, treatment, 48-hour visit, and 30-day follow-up.

### 5.3 STUDY POPULATION

The study population consists of subjects that have a PE. Subject eligibility is to be determined based on data available to the Investigator at the time of enrollment. Subjects must meet all inclusion and no exclusion criteria to be eligible for the study. Waivers will not be granted by the Sponsor regarding enrollment criteria. All subjects that complete the procedure and the follow-ups will be included in the analysis.

In this study, subjects will be categorized as follows:

**Screen Failure:** Any screened patient who does not meet the inclusion and exclusion criteria. No case report forms (CRFs) are required for these patients. All patients screened will be documented on the Screening/Enrollment Log.

**Enrolled Subject:** All patients who met the inclusion/exclusion criteria and in whom the FlowTriever2 Catheter is inserted into the vasculature. These subjects will comprise the "Enrollment Population."

**Intent-To-Treat (ITT):** All "Enrolled Subjects" in whom the procedure was attempted and the FlowTriever2 Catheter was deployed, whether successful or not.

**Modified Intent-To-Treat (mITT):** All subjects in the "ITT Population" who have no thrombolytics administered during the procedure.

**Full Analysis Set (FAS):** All subjects in the "mITT Population" that have successfully received the procedure and have completed the 48-hour post- procedure follow-up (+36 hours or discharge, whichever comes first) per study protocol.

**Completed Cases (CC):** All subjects in the "mITT Population" that have successfully received the procedure and have completed all follow-up visits.

FLARE-FT2 Study CONFIDENTIAL Page 26 of 60

### 5.4 STUDY ENROLLMENT CRITERIA

Only patients who meet all inclusion criteria and none of the exclusion criteria are considered eligible for enrollment. The decision to use the FlowTriever2 Catheter will occur prior to the procedure and written informed consent will be obtained prior to all study-specific procedures.

If the FlowTriever2 Catheter is not inserted into the vasculature, the subject is considered a screen failure (not meeting inclusion criteria for use of FT2) and is not enrolled nor entered into the EDC.

# 5.5 INCLUSION CRITERIA

Subjects must meet all the inclusion criteria to be considered eligible for enrollment including:

- 1. Age  $\geq$  18 and  $\leq$  75 years
- 2. Clinical signs and symptoms consistent with acute PE
- 3. PE symptom duration ≤ 14 days
- 4. CTA evidence of proximal PE (filling defect in at least one main or lobar pulmonary artery)
- RV/LV ratio of ≥ 0.9 (NOTE: Enrollment qualification assessment based on Investigator's interpretation of RV/LV ratio)
- 6. Systolic blood pressure ≥ 90 mmHg (initial SBP may be ≥ 80 mmHg if the pressure recovers to ≥ 90mmHg with fluids)
- 7. Stable heart rate < 130 BPM prior to procedure
- 8. Patient is deemed medically eligible for interventional procedure(s), per institutional guidelines and/or clinical judgment.
- 9. FlowTriever2 Catheter enters the vasculature

# 5.6 EXCLUSION CRITERIA

Subjects must not meet any of the following general exclusion criteria:

- 1. Thrombolytic use within 30 days of baseline CTA
- 2. Pulmonary hypertension with peak pulmonary artery pressure > 70 mmHg by right heart catheterization
- 3. Vasopressor requirement after fluids to keep pressure ≥ 90 mmHg
- 4. FiO2 requirement > 40% or > 6 LPM to keep oxygen saturation > 90%
- 5. Hematocrit < 28% (NOTE: hematocrit required within 6 hours of index procedure)
- 6. Platelets < 100,000/μL
- 7. Serum creatinine > 1.8 mg/dL
- 8. INR > 3
- 9. Major trauma Injury Severity Score (ISS) > 15
- 10. Presence of intracardiac lead in the right ventricle or right atrium placed within 6 months
- 11. Cardiovascular or pulmonary surgery within last 7 days
- 12. Actively progressing cancer
- 13. Known bleeding diathesis or coagulation disorder
- 14. Left bundle branch block
- 15. History of severe or chronic pulmonary arterial hypertension
- 16. History of chronic left heart disease with left ventricular ejection fraction ≤ 30%
- 17. History of uncompensated heart failure
- 18. History of underlying lung disease that is oxygen dependent
- 19. History of chest irradiation
- 20. History of heparin-induced thrombocytopenia (HIT)
- 21. Any contraindication to systemic or therapeutic doses heparin or anticoagulants

FLARE-FT2 Study CONFIDENTIAL Page 27 of 60

[figure not shown]
- 22. Known anaphylactic reaction to radiographic contrast agents that cannot be pretreated
- 23. Imaging evidence or other evidence that suggests, in the opinion of the Investigator, the Subject is notappropriate for mechanical thrombectomy intervention (e.g., inability to navigate to target location, predominately chronic clot, or non-clot embolus)
- 24. Life expectancy of < 90 days, as determined by Investigator
- 25. Female who is pregnant or nursing
- 26. Current participation in another investigational drug or device treatment study

# **6 FLARE-FT2 STUDY PROCEDURES**

# 6.1 OVERVIEW OF STUDY FLOW

Subjects presenting with PE will be evaluated by the Investigator, in accordance with their institutional practices, to establish an appropriate treatment plan based on the patient's medical condition and available diagnostic screening procedures prior to recruitment in the FLARE-FT2 Clinical Study. A representative overview of the study flow is shown in Figure 5.

FIGURE 5. Representative Study Flow from Screening to Discharge

# 6.1.1 SUBJECT SCREENING

Patients will be screened to determine their initial eligibility and interest in the study. Informed consent will be obtained once a patient has satisfied screening criteria and prior to any study-specific procedures not part of standard of care. All patients screened will be documented on the Screening/Enrollment Log.

FLARE-FT2 Study CONFIDENTIAL Page 29 of 60
Protocol 21-001

# 6.1.2 INFORMED CONSENT

Written, study-specific informed consent will be obtained from each patient via the current IRB-approved Informed Consent Form (ICF) prior to the patient's de-identified medical record or personal health information (PHI) being shared with any study representative. The Investigator will keep the original ICF and a copy will be given to the patient. The patients will be informed that they are free to refuse entry into the study and free to withdraw from the study at any time without prejudice to future treatment. The patients will also be informed about study purpose, alternative treatments, potential risks/benefits, and study assessment schedule.

# **6.1.3 NUMBERING OF STUDY SUBJECTS**

Each site will be assigned a site number at the beginning of the Study and each enrolled Subject will be assigned a sequential subject number. All Subjects who provide informed consent and have the study procedure will be given a unique subject number and the subject number will be recorded on the Screening/Enrollment Log. The subject number will consist of the site number followed by a sequential number that begins with "001."

### 6.1.4 IMAGING AND INVASIVE PRESSURE

# Computed Tomography Angiography (CTA)

The Study requires a CTA be obtained for subject screening to confirm pulmonary embolism and verify RV/LV ratio for inclusion.

# Invasive Pulmonary Artery (PA) Systolic Pressure

Once access is achieved, a pre-procedure invasive PA systolic pressure will be obtained prior to beginning the FlowTriever part of the procedure. After the FlowTriever System has been removed, a post-procedure invasive PA systolic pressure will be obtained to assess change between end mean and pulmonary arterial pressures and baseline.

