# **PROTOCOL SYNOPSIS**

Protocol Number	21-001			
Study Title	Fl owTriever Pulmon ary Embolectomy Clinical Study- F low T riever 2 (FLARE-FT2)			
Study Device	FlowTriever2 Catheter			
Regulatory Status	
 
Under US Regulations 510(k) number K201541, the FlowTriever2 Catheter is indicated for:         
 
The non-surgical removal of emboli and thrombi from peripheral blood vessels.
 
Injection, infusion, and/or aspiration of contrast media and other fluids into or from a blood vessel.
 
 
 
The FlowTriever2 Catheter is intended for use in the peripheral vasculature.
 
			
Sponsor	Inari Medical [name]			
Study Objective	The primary study objective is to evaluate the safety and effectiveness of the FlowTriever2 Catheter for the treatment of pulmonary embolism (PE).			
Study Population	This study will enroll 50 subjects			
Number of Sites	Five to twelve (5-12) sites will participate in the study			
Study Design	The FLARE-FT2 confirmatory study is a prospective, single-arm, multicenter study of the FlowTriever2 Catheter			
Safety Endpoints	
 
The study's primary safety endpoint is incidence of adjudicated Serious Adverse Events (SAE), which is a composite of:         
 
Mortality through 48 hours after the index procedure related to FlowTriever2 Catheter
 
Major bleeding through 48 hours after the index procedure related to FlowTriever2 Catheter
 
Intra-procedural device or procedure-related adverse events, including:

			

	The study's primary effectiveness endpoint is the change in mean pulmonary arterial pressure from baseline pre-procedure and post-procedure  The study's secondary effectiveness endpoints are:  The change in systolic pulmonary arterial pressure from baseline pre-procedure to post-procedure  Incidence of adjunctive thrombolytic use				
Effectiveness Endpoints					

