# 4.1 PRIMARY ENDPOINT - EFFECTIVENESS

The study's primary effectiveness endpoint is the change in mean pulmonary arterial pressure from baseline pre-procedure to post-procedure.

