**Table 1: Schedule of Assessments** 

Assessment/Method	Baseline	Procedure (Day 0**)	48-Hr Visit (+36 hours, or time of discharge, whichever comes first****)	30-Day Visit (-5 to +15 days)
Verification of inclusion/exclusion criteria	V			
Medical/Surgical History	V			
Physical Examination/Vitals	V		V	V
Blood Labs	V			
CT Angiography	√			
Invasive PA Pressure (x2)*		√		
Concomitant Medications***	√	√	√	√
Adverse Events		V	V	√

\*Invasive PA pressures required pre- and post-procedure

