#### 9.2 PRIMARY ENDPOINT - EFFECTIVENESS

The primary effectiveness endpoint will include an evaluation of the mean pulmonary arterial pressure changes between pre- and post-procedure.

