5.3. Primary Effectiveness Endpoint Analysis

The primary effectiveness endpoint analysis is performed by assessing the means, standard deviations, medians, and inter-quartile ranges of the mean pulmonary arterial pressure changes and/or percentage change between pre- and post-procedure.

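### Protocol 6.1.4 tells sites to take systolic PA pressure, but the primary effectiveness endpoint is change in mean PA pressure, and no collection instruction requires the mean

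*Protocol*

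**What the plan says.** **What sites are told to measure.** The relevant part of protocol 6.1.4 is headed "Invasive Pulmonary Artery (PA) Systolic Pressure". Before treatment, "a pre-procedure invasive PA systolic pressure will be obtained prior to beginning the FlowTriever part of the procedure". After the system is removed, "a post-procedure invasive PA systolic pressure will be obtained to assess change between end mean and pulmonary arterial pressures and baseline". Elsewhere the request is general. The Table 1 footnote reads "Invasive PA pressures required pre- and post-procedure", and the list of procedure assessments in protocol 6.2.2 likewise asks for invasive PA pressure at both times without naming a component.

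**What the analysis needs.** Protocol 4.1 states that the "primary effectiveness endpoint is the change in mean pulmonary arterial pressure from baseline pre-procedure to post-procedure". The synopsis and SAP 2.2 define the endpoint in the same terms. Protocol 9.2 plans "an evaluation of the mean pulmonary arterial pressure changes between pre- and post-procedure", and the summaries in SAP 5.3 include the "inter-quartile ranges of the mean pulmonary arterial pressure changes and/or percentage change between pre- and post-procedure". The change in systolic pressure is listed separately as a secondary endpoint (protocol 4.3 and 9.4; SAP 5.5), so the plan treats the two pressures as different variables.

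**The concern.** The one specific measurement instruction names the secondary variable and leaves out the primary one. Section 6.1.4 also disagrees with itself. Its heading and both instructions say systolic, while the closing clause, whose wording is garbled, gives a mean pressure as the reason for the reading.

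What is at stake is the only primary effectiveness variable. The reading is taken during the procedure and cannot be taken again later. Systolic alone does not give the mean, and neither document has a rule for deriving it from other readings. A site that wrote down systolic at both times could fairly believe it had complied. The deviation rule in protocol 10.1.4 is aimed at assessments that were not collected, so such a site might see nothing to report.

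**Working it through.** This is a comparison of text. The plan gives no sample size or power for the pressure endpoint, so there is no figure of its own to reproduce. The only design calculation is for safety (50 subjects, 11% against 25%, one-sided alpha 0.05, at least 80% power). An exact binomial check with success at 7 or fewer events gives alpha 0.0453 and power 0.8207, which agrees with it. Nothing here touches that calculation.

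**Step 1. The instruction.** In the pressure part of protocol 6.1.4, systolic is named three times (1 heading + 2 instructions) and mean once (closing clause).

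**Step 2. Every place that bears on the primary variable.**

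| Place | Role | Pressure named |
|---|---|---|
| Protocol 6.1.4 | tells sites what to take | systolic; mean only as the purpose |
| Protocol Table 1 and footnote | tells sites what to take | not specified |
| Protocol 6.2.2 list | tells sites what to take | not specified |
| Protocol synopsis | defines primary endpoint | mean |
| Protocol 4.1 | defines primary endpoint | mean |
| Protocol 9.2 | describes primary evaluation | mean |
| SAP 2.2 | defines primary endpoint | mean |
| SAP 5.3 | describes primary analysis | mean |

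Five places make the mean the primary variable. None of the three places that direct collection explicitly requires it to be recorded.

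**Step 3. Could the general wording or the safeguards supply the requirement?**

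- Protocol 6.2 makes the Table 1 examinations mandatory, but the Table 1 row does not say which pressure.
- Protocol 10.8 says the eCRFs cover all study data points, but it does not list them.
- Protocol 10.9 has monitors check CRF entries against source. That verifies values that were entered; it does not by itself show that an unspecified value is missing.

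Each is compatible with collecting the mean. None names it.

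**Step 4. Size, for one site that recorded systolic only.** Inputs from protocol 5.1: 50 subjects, and no site above 20% of enrolment.

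- Smallest loss: 1/50 = 2%.
- Largest loss: 0.20 × 50 = 10 subjects; 10/50 = 20%.

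This bounds the loss at a single site. It does not estimate how likely the loss is, and it does not bound the loss across the study if several sites read 6.1.4 the same way.

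**Step 5. What would happen to the missing values.** SAP section 4 fills missing pre- or post-procedure primary values by resampling the observed ones, assuming they are missing at random. If a whole site lacked the mean, its subjects would be represented by readings from other sites. The imputation completes the data set; it does not recover the measurements.

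**The case against.** The strongest reply is that the mean will be collected anyway. Data enter the study through the eCRF, which protocol 10.8 says was built to hold all study data and comes with completion guidelines. Sites are trained on the objectives, the protocol and the CRFs before any study procedure (10.3), and operators must already have treated PE with the FlowTriever System (10.4). Anyone trained on the protocol will have met section 4.1. The interim registry results in protocol 3.4 report an on-table mean PA pressure falling from 31.9 to 24.8 mmHg, so the mean has been collected with this system before. The closing clause of 6.1.4 points to the mean, and Table 1 is not limited to systolic. A mean may also sit in the procedure record, where monitoring and queries could retrieve it. Finally, missing values have a planned handling, and the endpoints are descriptive.

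Much of this stands. It makes loss of data a possibility rather than an expectation, and it means permanent loss cannot be assumed where the source record holds a mean. It also shows that the eCRF check should come first.

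It does not remove the defect. None of these provisions names the mean as a value to record. The closing clause states why a reading is taken, not what to write down, and a reader must set aside the heading and two plain instructions to find a requirement in it. The registry's practice does not show what this study's eCRF contains.

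**Conclusion.** The concern holds. The mismatch between the measurement instruction and the primary effectiveness endpoint is certain from the text. Its consequence is conditional. If a site records systolic only, the eCRF has no field for the mean and the source record holds none, that site's primary values are lost: 2% to 20% of the study per site. How many sites would be affected cannot be determined from the documents, and it may be none.

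The effect would be missing values in a descriptive primary summary. SAP section 2 says the endpoints do not determine study success, so no success decision changes, and neither do sample size, alpha or power. It should be corrected because the instruction, followed as written, does not yield the primary variable, and putting it right is a matter of wording.

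**What to change.** 1. Confirm now that the eCRF has a field for mean PA pressure at both the pre- and post-procedure times. This needs no amendment. If a field is absent, add it and query sites for any mean already in source.
2. In protocol 6.1.4, retitle the subsection *Invasive Pulmonary Artery Pressure*. Require both mean and systolic PA pressure before FlowTriever use and after removal, and replace the closing clause with *to assess change in mean and systolic PA pressure from baseline*.
3. Make the Table 1 row and the 6.2.2 list read *Invasive PA pressure (mean and systolic)*.

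A separate clerical correction, which carries no weight in this finding: SAP 2.4 labels the systolic change as the primary effectiveness endpoint under the secondary heading. Change that word to *secondary*.

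**Cost.** A wording-level protocol amendment, which under protocol 10.1.1 needs IRB approval at the 5 to 12 sites before use, and a one-word SAP revision. No procedure is added, because invasive pressure is already measured at both times.

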### 6.2 EXAMINATIONS

The following table details the clinical and laboratory procedures required from Screening through the 30-day follow-up visit. The majority of these tests and procedures are considered standard of care for all patients under treatment of clinically significant PE.

All scheduled exams listed in Table 1 must be performed at the designated time point and the results documented.

**Table 1: Schedule of Assessments** 

Assessment/Method	Baseline	Procedure (Day 0**)	48-Hr Visit (+36 hours, or time of discharge, whichever comes first****)	30-Day Visit (-5 to +15 days)
Verification of inclusion/exclusion criteria	V			
Medical/Surgical History	V			
Physical Examination/Vitals	V		V	V
Blood Labs	V			
CT Angiography	√			
Invasive PA Pressure (x2)*		√		
Concomitant Medications***	√	√	√	√
Adverse Events		V	V	√

\*Invasive PA pressures required pre- and post-procedure

# 6.2.1 BASELINE

Baseline assessments will include the following:

- Verification of inclusion/exclusion criteria
- Medical history
- Physical examination/vitals
- Blood labs
- CT angiography to confirm PE and RV/LV ratio for inclusion
- Concomitant medications

**Medical/Surgical History:** Relevant medical and surgical history will be collected from all consented subjects at the time of enrollment.

**Blood Labs**: The following blood values must be available to assess Subject eligibility for the study and for baseline data collection: hematocrit, hemoglobin, platelet count, serum creatinine, and International Normalized Ratio (INR).

**Concomitant Medications**: It is required that the subject's relevant concomitant medication use during the study be documented at pre-procedure, procedure, and follow- up visits.

FLARE-FT2 Study CONFIDENTIAL Page 31 of 60

\*\*Day 0 is the date of the FlowTriever procedure, Time 0 is when the FlowTriever2 Catheter enters the vasculature

\*\*\* Anticoagulation and Thrombolytics

\*\*\*\*If discharged prior to 48 hours from Index Procedure, phone call to subject will be conducted to confirm if any SAEs occurred between time of discharge and 48 hours.

As part of the routine care to treat PE, anticoagulation medication is administered to impede blood clotting and thrombolytic medication may be administered to dissolve blood clots. The specific dose and course of administration is at the discretion of the Investigator and will be recorded on the case report form (CRF).

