# 4.2 PRIMARY ENDPOINT - SAFETY

The study's primary safety endpoint is incidence of adjudicated Serious Adverse Events (SAE), which is a composite of:

- Mortality through 48 hours after the index procedure related to FlowTriever2 Catheter
- Major bleeding through 48 hours after the index procedure related to FlowTriever2 Catheter
- Intra-procedural device or procedure-related adverse events, including:
  - Clinical deterioration defined by hemodynamic or respiratory worsening
  - Pulmonary vascular injury related to FlowTriever2 Catheter
  - Cardiac injury related to FlowTriever2 Catheter

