# 6.2.3 48-HOUR FOLLOW UP (+36 HOURS, OR AT TIME OF DISCHARGE, WHICHEVER COMES FIRST)

The sites will complete the following assessments on the subjects at the 48-hour visit or at time of discharge, whichever comes first:

- Physical examination and vitals
- Record adverse events, as applicable
- Record concomitant medications

\*Note: If discharged prior to 48 hours from Index Procedure, phone call to subject will be conducted to confirm if any SAEs occurred between time of discharge and 48 hours.

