# 12 TERMS AND DEFINITIONS

Term	Definition	
	Primary Safety Definitions	
Clinical Deterioration	Clinical deterioration will include treatment-related events, such as unplanned endotracheal intubation, unexpected requirement for mechanical ventilation, arterial hypotension (>1 hour or requiring vasopressors) or shock, cardiopulmonary resuscitation, persistent worsening in oxygenation, and emergency surgical embolectomy.	
Device Related Death	Device-related death is defined as any death directly related to thedevice not performing as expected. Device-related death would include death from:  Vascular or cardiovascular injury  Device malfunction  Device-induced cardiac arrhythmia	
Life Threatening or Disabling Bleeding (VARC-2)	
 
Fatal bleeding, OR
 
Bleeding in a critical organ, such as intracranial, intraspinal, intraocular, or pericardial necessitating pericardiocentesis, or intramuscular with compartment syndrome, OR
 
Bleeding causing hypovolemic shock or severe hypotension requiring vasopressors or surgery, OR
 
Overt source of bleeding with drop in hemoglobin ≥5 g/dL or whole blood or packed red blood cells (RBCs) transfusion ≥ 4 units*
 
	
Major Bleeding (VARC- 2)	Overt bleeding that is:  Associated with a drop in the hemoglobin level of at least 3 g/dL, OR  Requires transfusion of 3 units of whole blood/RBC, OR  Causes hospitalization, permanent injury, or requiring surgery, AND  Does not meet criteria of life-threatening or disabling	
Minor Bleeding (VARC- 2)	Any bleeding worthy of clinical mention (e.g., access site hematoma) that does not qualify as life-threatening or disabling bleeding or major bleeding.	
Pulmonary Vascular Injury	Pulmonary vascular injury is defined as perforation or injury of a major pulmonary arterial branch during the index procedure requiring intervention, including but not limited to blood transfusion, open or endovascular intervention, to avoid permanent injury.	
Cardiac Injury	Cardiac injury is defined as any damage to the heart during the index procedure requiring intervention, including but not limited to blood transfusion, open or endovascular intervention, to avoid permanent injury.	
Additional Definitions		

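### Hemoglobin is scheduled only at baseline and transfusions not at all, so the numeric criteria for major bleeding cannot be applied systematically to every subject

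*Protocol*

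**What the plan says.** **The endpoint.** Protocol section 4.2 lists as a primary safety component: "Major bleeding through 48 hours after the index procedure related to FlowTriever2 Catheter". Section 12 of the protocol, repeated in SAP section 6, defines major bleeding as overt bleeding that meets one of three criteria. The first is "Associated with a drop in the hemoglobin level of at least 3 g/dL". The second is a 3-unit transfusion. The third is a clinical consequence: hospitalization, permanent injury or surgery. The bleed must also fall short of the life-threatening tier, which has its own numeric entry at a fall of at least 5 g/dL or at least 4 units.

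**The data collection.** Protocol section 6.2 presents Table 1 as the list of what is required: "The following table details the clinical and laboratory procedures required from Screening through the 30-day follow-up visit". Table 1 ticks blood labs at baseline only. Section 6.2.1 says of those labs: "The following blood values must be available to assess Subject eligibility for the study and for baseline data collection: hematocrit, hemoglobin". Section 6.2.3 introduces the next visit with "The sites will complete the following assessments on the subjects at the 48-hour visit or at time of discharge, whichever comes first", and the list that follows is examination and vitals, adverse events and medications. The Table 1 footnote limits concomitant medications to "Anticoagulation and Thrombolytics". For a subject who leaves before 48 hours, a "phone call to subject will be conducted to confirm if any SAEs occurred between time of discharge and 48 hours".

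**The concern.** A fall in hemoglobin needs two values, and the plan requires one. Transfused units decide both the major tier and its upper boundary, yet they have no place in the schedule. Whether an overt bleed is graded minor or major can then depend on whether a site happened to check hemoglobin and passed the result on.

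The reported incidence of this composite is the trial's main safety statement. SAP section 4 does provide for missing primary safety data, through worst-case and tipping-point imputation. That rule acts on data recognised as missing. Where no later hemoglobin is scheduled, its absence need not be flagged, and an ungraded bleed can enter the analysis as a subject without an event.

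**Working it through.** **1. The plan's own figure for this endpoint.** Protocol section 9.1 and SAP section 5.1 give at least 80% power with 50 subjects, 11% against a performance goal of 25%, one-sided alpha 0.05. With an exact binomial, the largest count c with P(X ≤ c | n = 50, p = 0.25) ≤ 0.05 is c = 7:
- P(X ≤ 7 | 0.25) = 0.0453
- P(X ≤ 7 | 0.11) = 0.8207

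The figure reproduces and is not in dispute. It takes for granted that every qualifying event is counted.

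**2. What each criterion needs, against what is scheduled.**

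| Needed to grade an overt bleed | Scheduled source |
|---|---|
| Hemoglobin before the procedure | Yes: protocol 6.2.1, Table 1 |
| Hemoglobin after the procedure, to 48 h | None: no labs in 6.2.2 to 6.2.5 |
| Red-cell units, to 48 h | None: no Table 1 row; medications limited to two drug classes |
| Hospitalization, permanent injury, surgery | Adverse event recording |

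Baseline hemoglobin has little other use. The blood-based exclusion criteria (protocol 5.6, items 5 to 8) are hematocrit, platelets, creatinine and INR. Apart from baseline description, the documents use hemoglobin only in the bleeding definitions.

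**3. The route that does exist.** Under protocol 8.2, adverse events include abnormal lab results, and the form records the action taken. Section 8.5 requires source documents for the event. Section 8.7 has the CEC adjudicate all adverse events, lets it ask for more source, and lets it overrule the investigator. Every step starts from a reported event, and none of them supplies a hemoglobin that was never drawn.

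**4. Direction.** An overt bleed that truly fell by 3 g/dL or more, with no later value and no other criterion met, falls into the minor tier or goes unreported. That lowers the rate. The reverse is possible: a bleed that is major through surgery or hospitalization, with an unmeasured fall of 5 g/dL or more, stays in the major tier although the definition would move it out.

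**5. Size per event.** 1/50 = 2.0 percentage points.

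**6. Illustration under an assumption.** Suppose the true composite rate is 25% and a share m of all composite events is missed. The documents give no value for m, so a range is shown. The expected observed rate is 0.25 × (1 − m).

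| m | Expected observed rate | P(7 or fewer events in 50) |
|---|---|---|
| 0 | 25% | 4.5% |
| 5% | 23.75% | 6.7% |
| 10% | 22.5% | 9.8% |
| 20% | 20% | 19.0% |
| 30% | 17.5% | 33.3% |

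This matters only to a reader who compares the result with 25%. The SAP plans no such test.

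**The case against.** The strongest reply is that a reader might infer the two criteria cannot be derived at all, and the documents do not support that. A reported bleed can be graded from the adverse event form, the source documents and the CEC's own requests. A site that calls a bleed minor does not keep it from the CEC. An overt bleed needing 3 units would very likely be a serious adverse event and be reported as one. All tiers require a recognised bleed, so a silent fall in hemoglobin is not a missed endpoint. This reply stands, and it limits the point to systematic ascertainment.

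Other tempting readings also go too far:
- **The bias can only favour the device.** The boundary at 5 g/dL shows an exception, as set out in the working. Downward is the main risk, not the only direction.
- **The FLASH registry shows that bleeding will drive this endpoint.** Its interim composite was 3/250 = 1.2%, all major bleeds (protocol 3.4). But protocol 3.3 counts bleeding there without a device restriction. This trial counts only bleeding related to the FlowTriever2 Catheter, and protocol 8.4 treats other devices, including the Triever Catheter, as ancillary. Many access-site bleeds may be attributed to the procedure or to an ancillary device and would not count in this component.
- **Early discharge measures the gap.** No subject has a required post-procedure value, whatever the day of discharge. Early discharge only adds reliance on a telephone call.
- **A formal decision is at risk.** SAP section 2 says the endpoints are descriptive and do not determine success.

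The eCRF and the CEC charter are not among the documents and may already hold these fields. That is a reason to check them. It does not answer the gap in Table 1.

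**Conclusion.** The point holds in this form: the hemoglobin and transfusion criteria cannot be applied in the same way to every subject from scheduled data. They depend on a site recognising and reporting an overt bleed, and on values drawn in routine care. The likelier consequence is a primary safety rate that is somewhat too low, with nothing in the data set to show it.

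The effect is 2 percentage points per missed qualifying event. The expected number of such events cannot be computed, because the documents do not say how many bleeds would be FlowTriever2-related or how many would turn on hemoglobin or units alone. The finding rests on Table 1 and sections 6.2.1 to 6.2.5 being the full schedule, as section 6.2 indicates, and on no further fields in the unseen eCRF. It is a worthwhile, inexpensive improvement to the ascertainment of a primary endpoint. It does not make the endpoint unusable.

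**What to change.** In protocol Table 1 and section 6.2.3, record for every subject:
- the lowest hemoglobin obtained in routine care from Time 0 to 48 hours or discharge, with date and time, or an entry of not done;
- the red-cell units transfused in the same period.

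Send to the CEC every subject with a fall of at least 3 g/dL from baseline or any transfusion, whether or not an adverse event was reported. The CEC then judges whether there was overt bleeding and whether it was related to the FlowTriever2 Catheter. In SAP section 5.2, report the number of subjects with no post-procedure hemoglobin beside the incidence. If the eCRF already holds these fields, cite them in Table 1 and add only the CEC trigger.

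The cost is two or three eCRF fields and a line in Table 1, with no added blood draw. The downsides are a few more CEC cases, possibly a slightly higher reported rate, and some subjects who will still have no value. The last of these will at least be visible.
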